### 10.1.2 Serious Adverse Events

A serious adverse event based on ICH and EU Guidelines on Pharmacovigilance for Medicinal Products for Human Use is any untoward medical occurrence that at any dose:

- Results in death (i.e., the AE actually causes or leads to death).
- Is life-threatening. Life-threatening is defined as an AE in which the subject was at risk of death at the time of the event. It does not refer to an event which hypothetically might have caused death if it were more severe. If either the Investigator or the IND Sponsor believes that an AE meets the definition of life-threatening, it will be considered life-threatening.
- Requires in-patient hospitalization >24 hours or prolongation of existing hospitalization.
- Results in persistent or significant disability/incapacity (i.e., the AE results in substantial disruption of the subject's ability to conduct normal life functions).
- Is a congenital anomaly/birth defect.
- Is an important medical event that may not result in death, be immediately life-threatening or require hospitalization, but may be considered an SAE when, based upon appropriate medical judgment, the event may jeopardize the subject or subject may require intervention to prevent one of the other outcomes listed in this definition. Examples of such events are intensive treatment in an emergency department or at home for allergic bronchospasm, blood dyscrasias, or convulsion that does not result in hospitalization; or development of drug dependency or drug abuse.

### 10.1.3 Severity Criteria (Grade 1-5)

Definitions found in the Common Terminology Criteria for Adverse Events version 4.03 (CTCAE v m 4.03) will be used for grading the severity (intensity) of *nonhematologic* AEs. The CTCAE v 4.03 displays Grades 1 through 5 with unique clinical descriptions of severity for each referenced AE. Should a subject experience any AE not listed in the CTCAE v m4.03, the following grading system should be used to assess severity:

- Grade 1 (Mild AE) – experiences which are usually transient, requiring no special treatment, and not interfering with the subject's daily activities

- Grade 2 (Moderate AE) – experiences which introduce some level of inconvenience or concern to the subject, and which may interfere with daily activities, but are usually ameliorated by simple therapeutic measures
- Grade 3 (Severe AE) – experiences which are unacceptable or intolerable, significantly interrupt the subject's usual daily activity, and require systemic drug therapy or other treatment
- Grade 4 (Life-threatening or disabling AE) – experiences which cause the subject to be in imminent danger of death
- Grade 5 (Death related to AE) – experiences which result in subject death

#### **10.1.4 Causality (Attribution)**

The Investigator is to assess the causal relation (i.e., whether there is a reasonable possibility that the study drug caused the event) using the following definitions:

**Not Related:**

Another cause of the AE is more plausible; a temporal sequence cannot be established with the onset of the AE and administration of the investigational product; or, a causal relationship is considered biologically implausible.

**Unlikely:**

The current knowledge or information about the AE indicates that a relationship to the investigational product is unlikely.

**Possibly Related:**

There is a clinically plausible time sequence between onset of the AE and administration of the investigational product, but the AE could also be attributed to concurrent or underlying disease, or the use of other drugs or procedures. Possibly related should be used when the investigational product is one of several biologically plausible AE causes.

**Related:**

The AE is clearly related to use of the investigational product.

#### **10.2 Unexpected Adverse Events**

An “unexpected” AE is an AE that is not listed in the Investigator's Brochure/package insert or is not listed at the specificity or severity that has been observed. For example, hepatic necrosis would be “unexpected” (by virtue of greater severity) if the Investigator's Brochure referred only to elevated hepatic enzymes or hepatitis. Similarly, cerebral thromboembolism and cerebral vasculitis would be “unexpected” (by virtue of greater specificity) if the Investigator's Brochure/package insert listed only cerebral vascular accidents. “Unexpected” also refers to AEs that are mentioned in the Investigator's Brochure as occurring with a class of drugs or as

anticipated from the pharmacological properties of the drug, but are not specifically mentioned as occurring with the study drug under investigation.

### **10.3 Documenting and Reporting of Adverse Events and Serious Adverse Events by Investigators**

#### **10.3.1 Assessment of Adverse Events**

Investigators will assess the occurrence of adverse events and serious adverse events at all subject evaluation time points during the study. All adverse events and serious adverse events whether volunteered by the subject, discovered by study personnel during questioning, detected through physical examination, clinically significant laboratory test, or other means, will be recorded. Each recorded adverse event or serious adverse event will be described by its duration (i.e., start and end dates), severity, regulatory seriousness criteria (if applicable), suspected relationship to the investigational product, and any actions taken.

If an adverse event is identified by the physician or staff during a non-evaluation time point the AE should also be recorded and reported in the manner by which all other AEs are processed.

#### **10.3.2 Adverse Event Reporting Period**

All AEs whether serious or non-serious, will be captured from ingestion of study drug until 30 days following the last dose of study drug.

Serious adverse events reported after 30 days following the last dose of study drug should also be reported if considered related to study drug. Resolution information after 30 days should be provided.

Progressive disease should NOT be reported as an event term, but instead symptoms/clinical signs of disease progression may be reported. All adverse events, regardless of seriousness, severity, or presumed relationship to study drug, must be recorded using medical terminology in the source document. All records will need to capture the details of the duration and the severity of each episode, the action taken with respect to the study drug, investigator's evaluation of its relationship to the study drug, and the event outcome. Whenever possible, diagnoses should be given when signs and symptoms are due to a common etiology (eg, cough, runny nose, sneezing, sore throat, and head congestion should be reported as "upper respiratory infection").

All deaths should be reported with the primary cause of death as the AE term, as death is typically the outcome of the event, not the event itself.

If a death occurs within 30 days after the last dose of study drug, the death must be reported as a serious adverse event.

### 10.3.3 Pregnancy

Before study enrollment, subjects must agree to take appropriate measures to avoid pregnancy. However, should a pregnancy occur in a female study subject, consent to provide follow-up information regarding the outcome of the pregnancy and the health of the infant until 30 days old will be requested.

A female subject must immediately inform the Investigator if she becomes pregnant from the time of consent to 90 days after the last dose of study drug. A male subject must immediately inform the Investigator if his partner becomes pregnant from the time of consent to 90 days after the last dose of study drug. Any female subjects receiving study drug(s) who become pregnant must immediately discontinue study drug. The Investigator should counsel the subject, discussing any risks of continuing the pregnancy and any possible effects on the fetus.

Although pregnancy itself is not regarded as an adverse event, the outcome will need to be documented. Any pregnancy occurring in a subject or subject's partner from the time of consent to 90 days after the last dose of study drug must be reported. Any occurrence of pregnancy must be reported to Pharmacyclics Drug Safety, or designee, per SAE reporting timelines. All pregnancies will be followed for outcome, which is defined as elective termination of the pregnancy, miscarriage, or delivery of the fetus. Pregnancies with an outcome of live birth, the newborn infant will be followed until 30 days old and this must be reported to Pharmacyclics Drug Safety, or designee, per SAE reporting timelines. Any congenital anomaly/birth defect noted in the infant must be reported as a serious adverse event.

### 10.3.4 Other Malignancies

All new malignant tumors including solid tumors, skin malignancies and hematologic malignancies will be reported for the duration of study treatment and during any protocol-specified follow-up periods including post-progression follow-up for overall survival. If observed, enter data in the corresponding eCRF.

### 10.3.6 Adverse Events of Special Interest (AESI)

Specific adverse events, or groups of adverse events, will be followed as part of standard safety monitoring activities. These events (regardless of seriousness) will be reported to KCI Drug Safety per the SAE reporting timelines.

#### 10.3.6.1 Major Hemorrhage

Major hemorrhage is defined as any of the following:

- Any treatment-emergent hemorrhagic adverse events of Grade 3 or higher\*. Any treatment-emergent serious adverse events of bleeding of any grade
- Any treatment-emergent central nervous system hemorrhage/hematoma of any grade

\*All hemorrhagic events requiring transfusion of red blood cells should be reported as grade 3 or higher AE per CTCAE v4.03.

Events meeting the definition of major hemorrhage will be captured as an event of special interest according to Section 10.3.6 above.

### **10.3.7 Expediting Reporting Requirements for Serious Adverse Events**

All serious adverse events and AESIs (initial and follow-up information) will be reported on FDA Medwatch (Form 3500A).

The initial report must be as complete as possible, including an assessment of the causal relationship between the event and the investigational product(s), if available. Information not available at the time of the initial report (e.g., an end date for the adverse event or laboratory values received after the report) must be documented on a follow-up MEDWATCH. A final report to document resolution of the SAE is required. The Pharmacyclics protocol number Ibrutinib PCI-32765 should be included on SAE reports to Pharmacyclics. A copy of the fax transmission confirmation of the SAE report to Pharmacyclics should be attached to the SAE and retained with the patient records. The principal Investigator is required to notify his/her Institutional Review Board (IRB) of a serious adverse event according to institutional policy.

**SAEs and AESIs must be reported within 24 hours of awareness of the event. Each site is responsible for reporting these events** to both Pharmacyclics and KCI via email or fax:

Pharmacyclics:

[[contact]](mailto:[contact])

[contact]

Karmanos:

[[contact]](mailto:[contact])

[contact]

All serious adverse events that have not resolved by the end of the study, or that have not resolved upon discontinuation of the subject's participation in the study, must be followed until any of the following occurs:

- The event resolves
- The event stabilizes

- The event returns to baseline, if a baseline value/status is available
- The event can be attributed to agents other than the study drug or to factors unrelated to study conduct
- It becomes unlikely that any additional information can be obtained (subject or health care practitioner refusal to provide additional information, lost to follow up after demonstration of due diligence with follow-up efforts)

#### **10.4 Reporting to Regulatory Agencies:**

Serious adverse events that are unlisted/unexpected, at least possibly associated to the study drug, and that have not previously been reported in the Investigators brochure, or reference safety information document will be forwarded to FDA by the IND holder (Karmanos) according to 21 CFR 312.32.

It is the responsibility of the Investigator and the research team to ensure that serious adverse events are reported according to the Code of Federal Regulations, Good Clinical Practices (GCP), the protocol guidelines, the sponsor's guidelines, and Institutional Review Board policy.

### **11 STUDY ADMINISTRATION AND INVESTIGATOR OBLIGATIONS**

### **12 DATA AND SAFETY MONITORING**

1. Scheduled investigator meetings will be held monthly or more frequently depending on the activity of the protocol. These meetings will include the protocol investigators and research staff involved with the conduct of the protocol.
2. During these meetings the investigators will discuss:
  - Safety of protocol participants (adverse events and reporting)
  - Validity and integrity of the data (data completeness on case report forms and complete source documentation)
  - Enrollment rate relative to expectation of target accrual, (eligible and ineligible participants)
  - Retention of participants, adherence to the protocol and protocol deviations
  - Protocol amendments
3. In addition, Data and Safety Monitoring Reports (DSMR) of the research meetings will be completed by the Study Coordinator from each site and submitted to the Karmanos Data and Safety Monitoring Committee (DMSC) monthly for review. **(See Appendix 5)** The DSMC will review safety of study subjects and will recommend continuation or closure of

the study. The DSMC will review the safety data quarterly and will recommend termination if they judge the rate and severity of AEs to be unacceptable. The DSMC's recommendations will guide study conduct.

4. The Barbara Ann Karmanos Cancer Institute, Data and Safety Monitoring Committee (DSMC) is composed of medical providers, pharmacists and research staff and provides the primary oversight of data and safety monitoring for KCI Investigator-initiated trials.

### **12.1 Institutional Review Board (IRB), Research Ethics Board (REB) and Independent Ethics Committee (IEC) Approval**

The protocol for this study has been designed in accordance with the general ethical principles outlined in the Declaration of Helsinki. The review of this protocol by the IRB/EC and the performance of all aspects of the study, including the methods used for obtaining informed consent, must also be in accordance with principles enunciated in the declaration, as well as ICH Guidelines, Title 21 of the Code of Federal Regulations (CFR), Part 50 Protection of Human Subjects and Part 56 Institutional Review Boards.

The Investigator will be responsible for preparing documents for submission to the relevant IRB/EC and obtaining written approval for this study. The approval will be obtained prior to the initiation of the study.

The approval for both the protocol and informed consent must specify the date of approval, protocol number and version, or amendment number.

Any amendments to the protocol after receipt of IRB/EC approval must be submitted by the Investigator to the IRB/EC for approval. The Investigator is also responsible for notifying the IRB/EC of any serious deviations from the protocol, or anything else that may involve added risk to subjects.

Any advertisements used to recruit subjects for the study must be reviewed and approved by the IRB/EC prior to use.

### **12.2 Informed Consent**

The Investigator must obtain informed consent of a subject or his/her designee prior to any study related procedures as per GCPs as set forth in the CFR and ICH guidelines.

Documentation of the informed consent process will be documented in the patient's records. The original consent form must be maintained in the Investigator's study files.

### **12.3 Protected Subject Health Information Authorization**

The collection and processing of personal data from subjects enrolled in this study will be limited to those data that are necessary to fulfill the objectives of the study. These data must be collected and processed with adequate precautions to ensure confidentiality and compliance with

applicable data privacy protection laws and regulations. Appropriate technical and organizational measures to protect the personal data against unauthorized disclosures or access, accidental or unlawful destruction, or accidental loss or alteration must be put in place. Study personnel whose responsibilities require access to personal data agree to keep the identity of study subjects confidential.

The informed consent obtained from the subject (or his or her legally acceptable representative) includes explicit consent for the processing of personal data and for the investigator to allow direct access to his or her original medical records for study-related monitoring, audit, IEC/IRB review, and regulatory inspection.

Exploratory biomarker and pharmacokinetic research is not conducted under standards appropriate for the return of data to subjects. In addition, the researchers cannot make decisions as to the significance of any findings resulting from exploratory research. Therefore, exploratory research data will not be returned to subjects or investigators, unless required by law. Privacy and confidentiality of data generated in the future on stored samples will be protected by the same standards applicable to all other clinical data.

#### **12.4 Study Files and Record Retention**

Investigational Study Drug Accountability for the drug is the responsibility of the local principal investigator. The investigator will ensure that the drug is used only in accordance with this protocol and Good Clinical Practice. Drug accountability records indicating the drug's delivery date to the site (if applicable), inventory at the site (if applicable), use by each patient, and disposal of the drug (if applicable and if approved by KCI) will be maintained by the clinical site.

Accountability records will include dates, quantities, lot numbers, expiration dates (if applicable), and patient numbers. Please refer to Section 5.4.1.3 for additional details.

All research study documents will be retained in accordance with E6 Good Clinical Practice: Consolidated Guidance as stated “Essential documents should be retained for a minimum of 2 years after the last approval of a marketing application in an ICH region and until there are no pending or contemplated marketing applications in an ICH region or at least 2 years have elapsed since the formal discontinuation of clinical development of the investigational agent. These documents will be retained for a longer period, however, if required by the applicable regulatory requirements or by an agreement with the sponsor.” It is the responsibility of the sponsor to inform the investigator/institution as to when these documents no longer need to be retained.

Iron Mountain (IM) storage facility provides long-term storage of research documents for Karmanos Cancer Institute, Clinical Trial Office.

#### **12.5 Study Monitoring/Audit Requirements**

Clinical trial data will be captured in OnCore's (Clinical Trial Management System) electronic data capture system. Site personnel will be trained on the eCRF system by the Karmanos OnCore administrator. Trial data entered in Oncore will be verified by source documentation.

CRFs should be completed by within 10 business days of the availability of clinical documentation of a study visit. Data clarification and queries should be completed within 7 working days of notification.

Each participating site will submit source documents to KCI's clinical trials office. A KCI CTO monitor specialist will remotely monitor essential clinical trial data. Frequency of monitoring will be based on accrual at a site but will occur at least once every 1 month if a patient has been enrolled.

Monthly screening and enrollment logs are to be sent to the KCI Lead Study Coordinator. If deemed necessary by the primary site or sponsor an audit team may review contracted site data and materials in an on-site review.

## **12.6     Investigator Responsibilities**

The investigator is responsible for ensuring that the clinical study is performed in accordance with the protocol, current ICH guidelines on GCP, and applicable regulatory and country-specific requirements. Good Clinical Practice is an international ethical and scientific quality standard for designing, conducting, recording, and reporting studies that involve the participation of human subjects. Compliance with this standard provides public assurance that the rights, safety, and well-being of study subjects are protected, consistent with the principles that originated in the Declaration of Helsinki and that the clinical study data are credible.

## **12.7     Protocol Amendments**

Per the IST Agreement, any amendments to the Protocol or Informed Consent Form protocol must be sent to Pharmacyclics for review and approval prior to submission to the IRB. Written verification of IRB approval will be obtained before any amendment is implemented.

## **12.8     Publication of Study Results**

Per the IST Agreement, the Investigator is required to submit to Pharmacyclics a copy of a planned publication (abstract, poster, oral presentation or manuscript) prior to the submission thereof for publication or disclosure. Pharmacyclics may provide scientific comments and suggestions understanding that the Investigator has sole editorial responsibility, and retains the authority to make the final determination on whether or not to incorporate Pharmacyclics comments or requests for additional information.

## **12.9     Study Discontinuation**

Per the IST Contract, the Investigator reserves the right to terminate the study at any time. Should this be necessary, the Investigator will arrange discontinuation procedures in partnership with Pharmacyclics. In terminating the study, the Investigator will assure that adequate consideration is given to the protection of the subjects' interests. Pharmacyclics may terminate

the study for reasons including, but not limited to: evidence that the PI or an involved investigator is unqualified to conduct research or fulfill sponsor responsibilities (e.g., is listed on a debarment or ineligible investigator list); failure to meet timelines or achieve agreed upon milestones; a known or perceived risk to patient well-being is identified; or breach of contract. Additional grounds for termination are outlined in the IST Agreement.

CONFIDENTIAL

**14 APPENDICES**

CONFIDENTIAL

# Appendix 1. Schedule of Assessments

Study Visits	Screening Phase	Treatment Phase (1 cycle = 28 days)								Suspected PD	Complete Remission	End-of-Treatment	Pre-PD FU		
		Cycle 1			Cycle 2		Cycles 3–7	Cycles 8–14	Cycles 15–Term						
		D1 (baseline)	D2	D15	D1	D15	D1	D1	D1						
Study Visit Windows	-28 days			± 3 days beginning cycle 2 day 1						Any time			+ 3 days	± 7 days	
Procedures															
Informed consent	x														
Medical history	x	x			x		x	x	x j	x			x		
Confirm eligibility k	x	x													
Tumor Biopsy	x f									x f					
Concomitant medications	x	x		x	x	x	x	x	x j				x		
Adverse events a		x		x	x	x	x	x	x j				x		
Study drug compliance review		x			x		x	x	x j				x		
Height	x														
Physical exam, vital signs, weight, ECOG	x	x		x	x	x	x	x	x j	x		x	x		
Disease assessment:															
PET/CT scan g	x						x g	x g	x g	x		x	x		
CT/MRI scan i	x i						x i	x i	x i	x i		x i			
Bone marrow biopsy/aspirate r	x										x				
Disease-related symptoms s	x	x			x		x	x	x j	x		x	x		
Overall response assessment							x g,i	x i,g	x i	x			x		
Hematology b	x	x		x	x	x	x	x	x j			x	x		
Serum chemistry c	x	x		x	x	x	x	x	x j			x	x		
Serum Pregnancy Test	x														
Creatinine clearance (Cockcroft-Gault)	x														
Biomarker serum samples		x e	x e	x e	x e					x e					
Hepatitis serologies d	x														
Coagulation panel h	x														
12-lead ECG x	x									If clinically indicated (e.g., subjects with palpitations, lightheadedness)					
Any new anticancer therapy													x		
Ibrutinib 560mg daily x 28 days dispensed p		x			x		x	x	x j						

D = day; Term = treatment termination; d/c = discontinuation; PD = progressive disease; FU = follow-up;

- a AEs are reported from the time the patient ingests study drug until 30 days following last dose of study drug. In addition to all routine AE reporting, all new malignant tumors including solid tumors, skin malignancies and hematologic malignancies are to be reported as adverse events for the duration of the study treatment and during any protocol-specified follow-up periods including post-progression follow-up for overall survival.
- b Hematology includes: complete white blood count with differential, hemoglobin, hematocrit, platelet count.
- c Serum chemistry includes sodium, potassium, calcium, albumin, glucose, creatinine, AST, ALT, alkaline phosphatase, LDH, total bilirubin, and Uric Acid.
- d Hepatitis B serologies include Hepatitis B IGG antibody, antigen and core antibody . If core antibody is positive the patient will need negative PCR to be eligible for study. Hepatitis C serologies include Hepatitis C IGG antibody.
- e Serial serum samples pre and post therapy will be assessed for Th1 ( (IFN-g ) and Th2 cytokines ( IL-10, IL-4 and IL-13) at 4 distinct time points (pre-dose cycle 1 day one, cycle 1 day 2 , cycle 1 day 15) , cycle 2 day 1 and at the time of progressive disease. All samples must be PRE-DOSE on date of draw. Utilize provided kits labeled per directions. Refer to Lab manual
- f Fresh tumor biopsy is highly recommended. The biopsy should be a lymph node excision whenever possible. If lymph node excision is not possible then core needle biopsies (minimum of 4 cores) are required. If fresh tumor tissue is unobtainable, a formalin-fixed paraffin embedded (FFPE) tumor block must be sent to the laboratory for correlative analysis.
- g PET/CT performed during screening, cycle 3 D1 (window of + or – 7 days) then at maximal tumor reduction on consecutive CT scans w/ contrast or at CR.
- h Coagulation panel includes PT, aPTT and INR
- i CT performed with contrast during screening, cycle 3 day 1 (+/- 7 day window) then every 12 weeks (+/- 7 days window) until cycle 15. Thereafter CT with contrast performed every 24 weeks (+/- 7 days)
- j Every odd cycle (Cycles 15, 17, 19, 21, 23, 25)
- k It is required that patients continue to meet eligibility on Day 1 of cycle 1 prior to dosing with the exception of the coagulation panel. If the subject met eligibility criteria for the coagulation panel during screening, it does not need to be repeated to re-confirm eligibility on C1D1.
- p Day 1 and 15 of C1 and C2 will be administered at the investigational site. Subsequently, day 1 of each cycle are taken on site until cycle 15. Beyond cycle 15 drug dispensation and clinic visits occur only on odd numbered cycles.
- r Bone marrow biopsy and/or aspirate is optional per investigator's decision at screening however if positive must be performed at CR
- s Disease-related symptoms include weight loss, fatigue, fever, night sweats, pruritis abdominal pain/discomfort due to splenomegaly including early satiety, and anorexia.
- x ECG's Must be performed at screening. ECG may be repeated at the investigator's discretion (e.g., palpitations, lightheadedness or new onset dyspnea).

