#### **7.1.1. Assessments**

- **Screening phase**
  - All patients must sign an informed consent prior to any study related procedures listed below with the exception of CT or PET imaging which can be performed prior to informed consent if done within 28 days of Day 1 of therapy.

- Screening procedures will be performed up to 28 days before first dose of study drug. Subjects must satisfy all of the inclusion and none of the exclusion criteria listed in Section 4.1 and Section 4.2, respectively, before receiving the first dose of study drug. The results of laboratory tests noted in the inclusion criteria must be within the limits specified prior to the first dose of study drug. Testing can be repeated for this purpose. The last result obtained prior to start of study treatment will be used to determine eligibility
- During the Screening Phase, eligibility criteria will be reviewed and a complete clinical evaluation will be performed (Appendix 1). A complete medical history and physical exam (including concomitant medications, vital signs, height, and weight) with baseline evaluation of lymphoma B-symptoms, adverse events and ECOG performance status (**See appendix 2**) will be conducted.
- 12 lead ECG
- All subjects must undergo a whole body FDG-PET scan and CT scan with contrast. Evaluation of other sites of disease, as relevant, may be performed. In instances where contrast cannot be utilized a discussion with the principal investigator is necessary.
- Laboratory studies including CBC with differential, Serum chemistries, hepatitis serologies, coagulation panels (**See Appendix 1**)
- Correlative biomarker analysis MUST be drawn prior to dose on cycle 1 day 1 of therapy (**See Lab Manual**)
- **A fresh tissue biopsy (excisional lymph node biopsy) is highly recommended for correlative analysis. In instances where an excisional lymph node biopsy is not obtainable, core needle biopsy (4 cores minimum) is recommended.**
- If fresh tumor biopsy is unobtainable, a formalin-fixed paraffin embedded (FFPE) tumor block must be submitted for correlative analysis. (**See Lab Manual**) For screening, a report confirming the diagnosis of Hodgkin's lymphoma is required.
- Subjects must initiate ibrutinib treatment within 28 days of the start of the screening phase
- **Treatment Phase**

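### The only scheduled pregnancy test can be 28 days old at the first dose, and footnote k does not clearly require a repeat on Cycle 1 Day 1

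*Combined protocol and SAP*

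**What the plan says.** Pregnancy status is an eligibility item twice over in the protocol. Section 4.1, item 6 (Ethical/Other) asks women of childbearing potential for a negative serum test at study entry. Section 4.2, item 19 (Concurrent Conditions) excludes pregnant women. The synopsis repeats both.

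In Appendix 1, the row "Serum Pregnancy Test" carries one mark, in the Screening column. The eligibility-confirmation row is marked at Screening and again at Cycle 1 Day 1 (C1D1), with a pointer to footnote k. That footnote has two sentences: "It is required that patients continue to meet eligibility on Day 1 of cycle 1 prior to dosing with the exception of the coagulation panel", and then "If the subject met eligibility criteria for the coagulation panel during screening, it does not need to be repeated to re-confirm eligibility on C1D1".

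Section 7.1.1 sets the timing. "Screening procedures will be performed up to 28 days before first dose of study drug", and "Subjects must initiate ibrutinib treatment within 28 days of the start of the screening phase". Subjects must satisfy every inclusion criterion and "none of the exclusion criteria listed in Section 4.1 and Section 4.2, respectively, before receiving the first dose of study drug". On laboratory results it adds "Testing can be repeated for this purpose" and "The last result obtained prior to start of study treatment will be used to determine eligibility".

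Section 4.1, item 7 covers contraception during therapy and for 90 days after the last dose. Section 10.3.3 asks subjects to agree before enrollment to avoid pregnancy, and to report any pregnancy from consent until 90 days after the last dose.

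**The concern.** The plan wants no pregnant woman to receive ibrutinib, but it schedules one pregnancy test, and that test may precede the first dose by four weeks. A woman who conceives after a negative Screening test could be dosed without anyone having departed from the schedule. No later visit in Appendix 1 has a pregnancy test, so no scheduled test would pick this up afterwards.

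The protocol itself recognises the hazard. Section 1.3.1 reports fetal loss and malformations in a rat study, and Section 10.3.3 requires a woman who becomes pregnant to stop the drug at once. Section 1.6 describes a young population, with a median age of 30 years, so women of childbearing potential can be expected to enroll. What is at stake is participant safety and uniform practice across sites.

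**Working it through.** No statistical model applies. The check is a reading of the timing rules and of which eligibility tests the schedule repeats.

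**1. Age of the result at first dose.** The Appendix 1 Screening window is -28 days, and both timing statements in Section 7.1.1 also give 28 days. The longest permitted gap between the scheduled test and the first dose is therefore 28 days. With a pre-dose window of 3 days, assumed here only as an example, the gap would be at most 3 days, which is 28 - 3 = 25 days shorter.

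**2. Scheduled tests before first dose.** Screening 1 + C1D1 0 = 1. With a C1D1 test added: 1 + 1 = 2.

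**3. What footnote k can mean.** The eligibility tests in Appendix 1 compare as follows.

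| Test | Eligibility basis | Screening | C1D1 |
|---|---|---|---|
| Hematology | 4.1, Laboratory item 1 | yes | yes |
| Serum chemistry | 4.1, Laboratory item 2 | yes | yes |
| Creatinine clearance | 4.1, Laboratory item 2 | yes | no, but can be recalculated from C1D1 creatinine |
| Coagulation panel | 4.1, item 3 | yes | no, excused by name |
| PET and CT | 4.1, Disease Related item 4 | yes | no |
| Hepatitis serologies | 4.2, item 10 | yes | no |
| Serum pregnancy test | 4.1, item 6; 4.2, item 19 | yes | no |

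Excusing one test by name suggests that the others are repeated. Taken literally, that would order a repeat PET and CT on C1D1, which the schedule plainly does not intend. The footnote can instead be read as asking that eligibility still hold, judged by the procedures marked that day. Both readings are open to a site. On the second, nothing marked at C1D1 tests for an early pregnancy, and pregnancy status cannot be derived from hematology or chemistry.

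**4. Whether another section closes the gap.**
- Section 7.1.1 allows repeat tests and relies on the last one. If none is repeated, the Screening result stands.
- Section 4.1, item 6 ties the test to study entry and gives no number of days before first dose.
- Section 4.1, item 7 does not name the interval from consent to first dose.
- Section 10.3.3 requires an agreement and a report, but no test, and gives no date on which contraception starts.
- Section 5.1 has the coordinating center approve the eligibility documents. A negative Screening result would satisfy that check.

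No section orders a pregnancy test on or shortly before C1D1.

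**5. Assays added by a C1D1 test.** One per woman of childbearing potential. The documents give no share of such women, so the range is 0 to 35, where 35 is the planned enrollment in Section 9.5.

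**The case against.** The strongest defense is that the protocol is coherent on either reading of footnote k. If the footnote orders everything but coagulation to be re-confirmed, a pregnancy re-check is already required and only a table mark is missing. If it asks for re-confirmation through the marked procedures, footnote and table agree. There are also safeguards: pregnancy is an absolute exclusion that must not apply before the first dose, medical history and eligibility are reviewed again on C1D1, and women agree to avoid pregnancy and to report it from consent. Study entry is undefined and is also the start of PFS in Section 9.3.2, so it could mean enrollment rather than any day of Screening. Finally, the eligibility checklist named in Section 5.1 and the consent form are not among the documents available here, and either could fix the timing.

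Much of this stands. A reader might infer that footnote k and the table contradict each other, with the footnote demanding a repeat test that the table omits. The documents do not support that, because PET, CT and hepatitis tests are also Screening-only and not exempted. A reader might also infer a known level of fetal risk at 560 mg. They do not support that either: Section 1.3.1 describes rat exposures approximately 6 and 14 times those of patients at 420 and 560 mg.

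What does not stand is the claim that the safeguards suffice. History, agreement and self-report depend on the woman knowing that she is pregnant, and they would not detect an unrecognised early pregnancy.

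**Conclusion.** The point holds as a safety gap with an ambiguous footnote. The protocol as written permits the first dose on a negative pregnancy result up to 28 days old, with one scheduled test before treatment and none after. Two sites could read footnote k differently and both could defend their reading.

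The conclusion rests on the schedule and text supplied; a checklist or consent form that fixes the test date would narrow it. The number of women affected cannot be estimated from the documents. The same Screening-only pattern for hepatitis serologies is noted, but this point is limited to pregnancy, which can begin within the window. There is no effect on the ORR, type I error, power or sample size. The change is recommended because it is cheap and protects participants.

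**What to change.** - **Appendix 1:** add a C1D1 mark to the serum pregnancy row, with a footnote requiring a negative serum result in women of childbearing potential on C1D1 or within a short stated window before the first dose. The length is for the sponsor to choose; 3 days is only an example.
- **Footnote k:** name the serum pregnancy test as one that is repeated, so that it is not left to inference.
- **Section 4.1, item 6, and the synopsis:** require the negative test both at Screening and before the first dose.
- **Section 4.1, item 7, and the synopsis:** start contraception at consent, matching the reporting period in Section 10.3.3. This is needed as well because a C1D1 test can miss a very recent conception.

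The cost is at most one additional assay per woman of childbearing potential, on blood already drawn at C1D1 for hematology and chemistry, and possibly a short wait for the result. A pre-dose window avoids that wait but may need a separate draw. The contraception start date adds no procedure. The rest is wording.
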